8.10 Safety Follow up

Adverse events and device deficiencies will be assessed at all visits, planned and unplanned. Subjects are followed through termination of the investigation (Visit 3). Any ongoing ADEs or SADEs at study termination will be followed until resolution. All subjects are encouraged to contact the Principal Investigator, or designee, if they experience problems that they believe are related to their investigational device or participation. This is to ensure that any device-related events are documented and to safeguard the subjects' health.

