19.1 Adverse events

An adverse event is any untoward medical occurrence, unintended disease or injury, or untoward clinical signs (including abnormal laboratory findings) in subjects, whether related to the investigational medical device(s) or the comparator(s), or the procedures involved. The adverse event shall be marked with the intensity mild, moderate, or severe. This could include events such as headache or dizziness.

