19.2 Adverse device effect

An adverse event, which is related to the use of the investigational medical device, is an adverse device effect, and should be marked as unlikely related, possible related, probable related or with causal relationship on the adverse event form.

The definition of an adverse device effect includes any event resulting from insufficiencies or inadequacies in the instruction for use, deployment, or any malfunction of the medical device, as well as any event resulting from use error or from intentional misuse of the device.

Table 2 lists anticipated adverse device effects that may occur.

Table 19-1 Anticipated adverse device effects and their likely incidence rates

ANTICIPATED ADE	INCIDENCE RATE
Urinary tract infection	Very unlikely
Macroscopic haematuria	Unlikely
Macroscopic leukocytes	Unlikely
Stinging and pain in urethra during catheterisation	Likely
Irritation of mucosa	Likely

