19.7 Investigator's reporting responsibilities

PI at each site must assess all (S)AE's that occur at his/her site.

- All serious adverse events and serious adverse device effects must be reported to sponsor within 24 hours of the site becoming aware of the event.
- A device deficiency that could have led to a serious adverse event but did not because suitable action was taken, intervention had been made or because of fortunate circumstances should be reported to sponsor within 24 hours of the site becoming aware of the event.
- New findings and/or updates in relation to already reported serious events should also be reported to sponsor within 24 hours of the site becoming aware of the event.
- Device deficiencies and all adverse device effects related to CE marked Coloplast investigational device and/or comparator must be reported to sponsor within 24 hours of becoming aware of the event.

When reporting the SAE, the relationship to the test material shall be described whether the event is considered

- **Not related**, the event has no temporal relationship with the use of the test material or the procedures.
- **Unlikely related**, the relationship with the use of the test material seems not relevant and/or the event can be reasonably explained by another cause, but additional information may be obtained.
- **Possible related**, the relationship with the use of the test material is weak but cannot be ruled out completely. Alternative causes are also possible (e.g. an underlying or concurrent illness/ clinical condition or/and an effect of another device, drug or treatment). Cases where relatedness cannot be assessed, or no information has been obtained should also be classified as possible.
- **Probable related**, the relationship with the use of the test material seems relevant and/or the event cannot reasonably be explained by another cause, but additional information may be obtained.
- **Definitely related/Causal relationship**, the event has a temporal relationship with the test material use/application or procedures.

and the intensity of the event should be considered, as such:

- **Mild**, the intensity of the event is mild with no further action or intervention
- **Moderate**, the intensity of the event will lead to an action or intervention to solve the event
- **Severe**, the intensity of the event will lead to follow up on the action or intervention, as the effect of the action or intervention may not decrease the symptoms.

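### The adverse-event intensity scale in 19.7 gives no criterion for symptom strength, so an intense event that needs no intervention has no matching grade.

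*Combined protocol and SAP*

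**What the plan says.** Section 19.1 makes grading compulsory for all adverse events, without defining the grades: "The adverse event shall be marked with the intensity mild, moderate, or severe".

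Section 19.7 holds the only definitions:

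- For Mild, the condition is that "the intensity of the event is mild with no further action or intervention".
- For Moderate, something has to be done to resolve the event.
- For Severe, the condition is that "the intensity of the event will lead to follow up on the action or intervention", and the reason given is "as the effect of the action or intervention may not decrease the symptoms".

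These definitions complete a sentence that begins with serious events only: "When reporting the SAE, the relationship to the test material shall be described whether the event is considered".

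Table 19-1 in section 19.2 lists five anticipated device effects. Two are rated Likely: irritation of mucosa, and "Stinging and pain in urethra during catheterisation".

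Section 11.7 plans to list and/or summarise adverse events. It names no test and no tabulation by intensity.

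**The concern.** An intensity grade should say how strong an event was. None of the three definitions gives a yardstick for that. The steps above Mild depend on whether someone acted and whether the action was followed up, so the grade partly records care given.

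This touches the events the sponsor most expects. Section 9.2 names discomfort or stinging in the urethra during catheterisation as a study risk. Such an event may be strong, short and over before anyone intervenes.

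The distortion could also differ between devices. The study is open label. Section 8.10 encourages men to contact the site about problems they attribute to their investigational device, and 19.2 defines an adverse device effect by reference to the investigational device. If contact, action or follow-up is more frequent with one catheter, a scale keyed to action carries that difference into the grades even when the symptoms are equally strong.

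**Working it through.** No arithmetic applies to the scale itself. I took four combinations of felt intensity and response and compared each with the 19.7 definitions.

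| Event | Mild? | Moderate? | Severe? | Result |
|---|---|---|---|---|
| Weak, no action | Yes | No, no action follows | No, nothing to follow up | Mild |
| Strong, no action | No, intensity is not mild | No, no action follows | No, nothing to follow up | No grade fits |
| Weak, treated, routinely rechecked | No, an action was taken | Yes | No, the recheck is not prompted by doubtful relief | Moderate |
| Strong, treated, followed up because relief is doubtful | No | Superseded | Yes | Severe |

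The second row is the gap. An investigator who must tick one of three boxes has only Mild left, as a default and not because the definition is met. The third row is the opposite error: a weak symptom leaves Mild as soon as it is treated.

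The boundary between Mild and Moderate is also unclear. Section 9.1 says mild pain or bleeding will be discussed with the healthcare professional. Whether that discussion is an action under 19.7 is not stated, so the same event could be graded differently across the 8 to 11 sites in up to four countries (section 7).

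How far do other measures cover the gap?

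- Discomfort VAS (6.2.4, 8.6, 8.8): rated after self-catheterisation at V2 and V3, in a subgroup of at least 42 of 72 men. Up to 72 − 42 = 30 men have no such rating.
- In the subgroup, the VAS covers one self-catheterisation per device. Section 5.7 plans 28 days × 6 catheters = 168 catheterisations per man in the home period with the investigational device (72 × 168 = 12,096, the plan's own total).
- Perception questionnaire (8.6, 8.8, Appendix A): not limited to the subgroup. It includes items on pinching or stinging, resistance and a blocking sensation, as agreement ratings given at the visit that closes each period. It does not grade individual events.

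For a single event during home use, the adverse-event grade is therefore the only intensity grading the plan defines.

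**The case against.** The best defence is that all three definitions name the intensity of the event, and that Moderate and Severe make it the reason for acting or following up. This stands as far as it goes: intensity is not ignored. What is missing is any criterion for judging it apart from the response.

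A reader might infer that the text positively classes intense untreated pain as Mild. It does not. Mild requires the intensity to be mild, so such pain has no matching grade.

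A reader might also infer that any minor symptom becomes Severe once it is treated and rechecked. The closing clause of the Severe definition prevents this: the follow-up must arise from the event's intensity, because the action may not relieve the symptoms. A routinely rechecked minor event is Moderate.

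Nor does 8.10 make open device effects Severe. It says: "Any ongoing ADEs or SADEs at study termination will be followed until resolution". That follow-up is triggered by the event being ongoing, not by its intensity. Section 19.5 describes follow-up after termination differently, and the two sections must be reconciled, but neither sets a grade.

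Finally, it would be too strong to say that a difference in discomfort between catheters would be hidden. The VAS and perception questions are compared by mixed models under 11.6. They capture discomfort in part, within the limits shown above.

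**Conclusion.** The concern holds in a limited form. The scale is not exhaustive: a strong event with no intervention has no grade, and a weak event that is treated cannot be Mild. Intensity in the listings is confounded with action taken.

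The consequence is confined to descriptive safety data. The primary and secondary endpoints, sample size, power and type I error do not use the scale, and reporting of serious events rests on the seriousness criteria in 19.4. The number of misgraded events cannot be estimated from the plan.

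Three assumptions apply. First, some of the anticipated stinging, pain or irritation will be strong yet untreated; this is a reasonable inference, not a figure in the plan. Second, contact and follow-up could differ by device; the open-label design allows this but does not show it. Third, no further definition of intensity stands in text next to 19.7 that was missing from the copy available to me. The point is worth correcting because it is specific and cheap to correct.

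**What to change.** In 19.7, define the three grades by symptom strength or tolerability, with or without interference with usual activities. Interference should not be the only anchor: strong pain confined to one catheterisation may disturb nothing afterwards and would again be graded Mild. The wording should let brief, intense pain be graded above Mild.

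Record action taken and follow-up as separate eCRF fields, if they are not already; the adverse-event form is not in the document. State in 19.7 that the scale applies to all adverse events, as 19.1 requires, and not only when a serious event is reported.

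The cost is protocol wording, eCRF completion guidance and brief site retraining. No visits, procedures or subjects are added.

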19.8 Sponsors reporting responsibilities

It is the responsibility of sponsor to ensure that the following are reported to national regulatory authorities immediately, but no later than 7 calendar days following the date of awareness by sponsor.

- All serious adverse events.
- All serious device effects.
- All device deficiencies that could have led to serious adverse events but did not because suitable action was taken, intervention had been made or because of fortunate circumstances.
- New findings and/or updates in relation to already reported events.

If the serious adverse event results in imminent risk of death, serious injury, or serious illness that requires prompt remedial action for other subjects, users or other persons or a new finding to such a serious adverse event, sponsor must immediately but no later than 2 calendar days after awareness by sponsor report the event to national regulatory authorities.

It is the responsibility of sponsor to inform all investigators in writing within 10 working days if device deficiencies, adverse events, adverse device effects, near-incidents, serious adverse events, serious adverse device effects or unanticipated serious adverse device effects lead to corrective actions (e.g. change of IFU).

20 Suspension or premature termination of the clinical investigation

Sponsor may suspend or prematurely terminate an investigation site or the entire clinical investigation for documented significant reasons.

If a suspicion of an unacceptable risk to subjects develops during the clinical investigation, sponsor will suspend the investigation while the risk is assessed. Sponsor will terminate the investigation if an unacceptable risk is confirmed. Sponsor will ensure that the premature termination will be justified in writing and will promptly inform the regulatory authorities and relevant EC(s). If monitoring or auditing of the clinical investigation identifies serious or repeated deviations at one of the participating investigation sites, sponsor will suspend or terminate the particular investigational site. The sponsor or investigator will inform the regulatory authority as appropriate and notify the EC about the termination of the site.

21 Clinical investigation report

At completion of the investigation, sponsor is responsible for writing the clinical investigation report. The report is retained on file. The report contains a critical evaluation of all data, which have been collected during the investigation. The report describes the methodology and design and a data analysis, including statistical preparation and conclusion.

Sponsor and national coordinating investigators must sign the final version of the clinical investigation report or an affidavit, indicating their agreement with the contents. If no coordinating investigators are appointed, then the signatures of the principal investigators should be obtained.

The clinical investigation report will be submitted to Ethics Committee and local regulatory authorities.

22 Publication policy

Coloplast, sponsor, is referring to the internal document 'Clinical Publication Policy' that will be available for internal and external persons involved in the publication process.

The investigation will be registered in a publicly accessible database before recruitment of the first subject. The results of the investigation, positive as well as inconclusive and negative will be published in the same publicly accessible database. The subjects' identity will remain confidential. Publication of results in the database will be conducted per the law of personal data protection and will be initiated as soon as scientifically acceptable, however, within one year after the last subject has completed the investigation. Data from the investigation is considered confidential until it is published per the conditions of this Clinical Investigation Plan and the 'Clinical Publication Policy'. Sponsor may publish anonymous single subject case stories (or public, if the subject consents) at any time during and after the investigation. The identification of the participant must not be possible. Sponsor reserves the right to use the data (published and unpublished) for reimbursement or regulatory purposes.

23 Suspension/termination of the clinical investigation

Sponsor will withdraw from sponsorship of the clinical investigation if

- major non-adherence to the clinical investigation plan is occurring
- it is anticipated that the subject recruitment will not be adequate to meet the investigation objectives at least 75% of the subjects should be entered within the recruitment time.

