Clinical Investigation Plan

CP334

A confirmatory, multi-centre, randomised, open label, controlled study confirming performance of a single-use intermittent micro-hole zone catheter in a population of adult male intermittent catheter users.

August 2022 – January 2023

Date: 2023-03-24

NCT05485935

CHANGE LOG

VERSION NUMBER	ISSUED BY (INITIALS)	COMMENTS (MAJOR CHANGES SINCE LAST REVISION)
1.0		
2.0		
• Sec 6.6: Reference to section 13.1.1. – corrected into 12.1.1• Sec 6.2.6: leukocyturia and specific gravity added• Appendix A added
3.0		Correction of flowchart formatting
4.0		Typos and minor corrections to ease understanding
5.0		Assessment "Other" added in section 6.2.5 due to analysis method

This confidential document is the property of Coloplast A/S.
No unpublished information contained herein may be
disclosed without written approval of Coloplast A/S.

Synopsis of the clinical investigation

Title:

A confirmatory, multi-centre, randomised, open label, controlled study confirming performance of a single-use intermittent micro-hole zone catheter in a population of adult male intermittent catheter users.

Test device and comparator:

The investigational device (test device) is a catheter for single use only and is intended to be used for drainage of the bladder through the urethra. The device is a new flexible single-use intermittent micro-hole zone catheter, which comes in two different sizes - size CH12 and CH14 - for male catheter users. The devices will be provided by Coloplast A/S, Denmark.

The comparator will be single-use hydrophilic sleeved soft/flexible catheters, of brand/type Hollister VaPro or Coloplast SpeediCath Flex, in the sizes CH12 or CH14. As the comparator devices are already on the market and will be used within the intended use in this investigation, it is not considered an investigational device.

Intended use:

The investigational device is a urinary catheter for intermittent use, available in the sizes CH12 and CH14. The catheter is intended for transient (less than 60 minutes) intermittent drainage of the bladder.

Objectives:

[figure not shown]
The primary objective is to demonstrate superior performance of the micro-hole zone catheter compared to a conventional 2-eyelet catheter through an improved bladder emptying.

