7.2.3 Hospital records

The recruitment method will be through subject records kept at the investigational site by the investigator or by use of the recruitment company Trialbee.

Trialbee send out general campaigns via online social media asking users of Coloplast products to sign up at the Coloplast consumer database if they are interested in being contacted for user-interviews or clinical trial participation. If interested in clinical trial and they use a catheter Trialbee contacts the user investigating whether the user match CP334. This is done by use of a study specific Nurse Script.

When the investigator has identified a potential subject from either own subject pool or has been provided a list of potential eligible subject via Trialbee platform, the investigator will contact the subject by sending them, by mail or e-mail, the written subject information, and a piece on the subjects' rights in research projects within health sciences, which they are encouraged to read. If the subject is interested in participating, he is encouraged to contact the site and an information meeting is arranged. Follow-up by phone will be done by the site (Informed consent process, section 17 and clinical investigation-related procedures, section 8.1).

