8.5 Test Period 1 (T1)

The four weeks of home-use with the first randomly assigned device according to an individual usage regime, include a 2-week run-in phase, followed by another 2 weeks of daily dipstick-test for haematuria, once daily after the first catheterisation in the morning. Result from dipstick should be recorded every day.

Follow-up/start dipstick-call: The nurse will call the subject when it is time to start the daily dipstick-testing.

8.6 Visit 2 (V2) – Catheterisation, follow-up and introduction to Test Period 2 (T2)

NB! To the extent possible, the subject should not have changed their medication the last 24 hours before V2.

- Assessment on user perception of catheter use and quality of life for Test Period 1. Study nurses to ensure the test subjects fill out the relevant questionnaires at the visit.
- Subgroup: Two catheterisations with the device used in T1 will be performed i.e., one by a healthcare professional and one by the user. Both followed by dipstick-test for haematuria, leukocyturia and specific gravity. All catheterisations will be performed in the same body position at all visits.
- Subgroup: Intake of fluid and waiting in the waiting room to ensure there is urine in the bladder before the second catheterisation.
- Subgroup: Assessments pertaining to performance will be recorded, including pressure measurements. This will be done immediately after each catheterisation.
- Subgroup: Three repeated measurements of residual volume will be measured with BladderScan i10 after each catheterisation is completed.
- Subgroup: After self-catheterisation, subjects are asked to assess any level of discomfort during catheter insertion, during emptying of bladder, at the end of emptying and at withdrawal of catheter (evaluated by VAS score). VAS scores are asked to be rated immediately after withdrawal of catheter.
- Dipstick-test for haematuria, leukocyturia and specific gravity after each catheterisation.
- Subgroup: Urine from both catheterisations will be collected for laboratory analysis on biomarkers (DK only).
- Introduction to 2nd randomly assigned device, including IFU.
- Instruction in recording results from stix of urine the last two weeks of T2

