12.1 Data collection and data management

12.1.1 Data Collection in the clinical investigation

Data management and statistical analyses are carried out by Medical Affairs, Coloplast A/S.

Data will be collected through an electronic data capturing (EDC) system on electronic Case Report Forms (eCRF), a secure, internet-based case report form. This system will be used to record all subject information collected in the investigation for secure data tracking and centralised data monitoring (“remote monitoring”) done by monitors, as defined in the monitoring plan.

The EDC system used is Rave EDC, version 20121.1.4, delivered by Medidata Solutions Inc. The system is designed to be compliant with the FDA requirements of 21 CFR part 11. It is a validated data management system allowing only qualified and trained personnel to enter the system. The system has full audit trail and electronic signature.

The sponsor will be responsible for training the investigator or delegate, in completion of the eCRF.

Principal Investigator, or delegate, at the clinical site will perform primary data collection directly into the eCRF or drawn from source-document (i.e. paper CRF, medical records etc. according to the Source Data

Specification Form) reviews. The eCRF will be completed on a continuous basis starting from the point of enrolling the subject to final follow up.

The eCRF will be completed by the investigator, or delegate, who have signed the Site Personnel Signature and Delegation List and Clinical Investigation Training Log. It will be the responsibility of the investigator to ensure that all measurements and observations are correctly noted in the eCRF.

All assessments and observations throughout the investigation for each subject must be carefully recorded in an eCRF during the visit or immediately after. The eCRF makes it possible to enter data right away when they are obtained. This is the preferred way of collecting data. In case this is not possible the data should be entered no later than 7 days after the visit / procedure.

Subject reported outcomes (Perception questionnaire, the quality-of-life questionnaire (Qualiveen), VAS scale and dipstick results during the two weeks of home use) will be completed by the subject in a paper CRF and entered into the eCRF by site personnel. After completion of the VAS scale by subject, the site personnel will measure the VAS-scale and enter the measurement in the eCRF.

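### Section 22 permits single-subject case stories during this open-label trial, while other men may still be recording their own secondary and exploratory outcomes

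*Combined protocol and SAP*

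**What the plan says.** Section 22 (Publication policy) contains three sentences that bear on this:

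- a general rule: "Data from the investigation is considered confidential until it is published per the conditions of this Clinical Investigation Plan" (and of an internal publication policy);
- a permission directly after it: "Sponsor may publish anonymous single subject case stories (or public, if the subject consents) at any time during and after the investigation";
- a condition on identity: "The identification of the participant must not be possible".

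The title describes "A confirmatory, multi-centre, randomised, open label, controlled study confirming performance", so each man knows which catheter he is using.

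Under section 8.5, home use in the first test period has a two-week run-in, "followed by another 2 weeks of daily dipstick-test for haematuria, once daily after the first catheterisation in the morning". Section 8.7 repeats this for the second period. Section 6.2.2 takes both secondary endpoints (red blood cell concentration and positive haematuria) from these readings. Section 12.1.1 says who records them: the subject-reported outcomes, including "VAS scale and dipstick results during the two weeks of home use) will be completed by the subject in a paper CRF", are then entered in the eCRF by site staff. The quality-of-life and perception questionnaires are handled in the same way.

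Sections 7.2.3 to 7.2.5 describe recruitment from site records, through a recruitment company's social-media campaigns "asking users of Coloplast products to sign up at the Coloplast consumer database", and, if needed, through the sponsor's own subject database and newspaper advertisements.

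**The concern.** A confirmatory open-label trial already depends on subjects reading and scoring without regard to the device they know they have. A published account of another participant's experience, chosen by the sponsor, gives them a further reason to expect one device to do better. If it reaches men who still have dipsticks to read or questionnaires to complete, their answers may move towards that expectation.

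What is at stake is the credibility of the secondary haematuria comparison and of the exploratory subject-reported outcomes. The exposure is avoidable: the plan permits it by an explicit sentence and gives no scientific reason for needing stories before the data are complete.

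**Working it through.** The plan gives no figure for this point, so the check sets the passages side by side, with simple counts and timing.

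**1. Does the confidentiality rule block the stories?** No. It holds data confidential until they are published on the plan's own terms, and the next sentence supplies such a term. The identity condition limits who may be recognised. It does not limit content or timing. Section 22 states no embargo, content limit or approval step for case stories.

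**2. Is there overlap in time?** Inputs: recruitment of about 10 weeks (section 7.2.2) and about 9 weeks per man (section 8.1).

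- First man enrolled at week 0 finishes at about 0 + 9 = week 9.
- Last man enrolled at about week 10 finishes at about 10 + 9 = week 19.
- A story about the first completer could therefore coincide with up to 19 − 9 = 10 weeks of other men's data collection.

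Section 22 does not require the man in the story to have finished, so an earlier story is also permitted.

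**3. Which outcomes do subjects record themselves?**

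| Outcome | Status | Who supplies it |
|---|---|---|
| Home dipstick: red cell concentration and positive haematuria; 14 days × 2 periods = 28 scheduled readings per man | Both secondary endpoints | All subjects |
| Quality-of-life index | Exploratory | All subjects |
| Perception questionnaire Part I: 5 handling + 10 confidence and control + 5 sensation + 2 satisfaction = 22 items | Exploratory | All subjects |
| Discomfort: 4 visual analogue scales | Exploratory | Subgroup of at least 42 |

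**4. How exposed are the primary endpoints?** Residual volume at first flow-stop and the number of flow-stops are derived from the catheterisation profile recorded during catheterisation by a healthcare professional (section 6.2.1). Two specialists analyse the raw scale and pressure data independently (section 12.1.1). Section 11.10 rests pass or fail on these two endpoints alone. The subject does not score either of them.

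**5. Would the analysis remove a shift?** The secondary models in section 11.5 have visit and device as fixed effects, and subject and subject-by-device as random effects. A shift common to both devices at a visit would go into the visit term. A shift that favours one device would go into the device term, which is the estimate of interest. The crossover does not cancel it.

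**The case against.** The strongest reply is that this is a hypothetical risk at the margin of the trial. Men already know their device, and section 17 has them told the aim, so the added effect of a story is unknown. Section 22 speaks of case stories, not trial results, and names no channel. The internal publication policy may already restrict timing. All of this stands, and it limits the weight of the point. It does not remove the permission written in the plan.

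A reader might infer more than the documents support:

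- **That the pass/fail result is compromised.** Step 4 of the working shows why it is much less exposed.
- **That stories would appear in the recruitment channels.** This is plausible, but section 22 does not say so, and men are also recruited from site records.
- **That stories would change who enrols.** The first completer finishes at about week 9 of a 10-week recruitment, which leaves about 10 − 9 = 1 week. Only a story about a man still in the trial could act earlier. The within-subject comparison also limits bias from who enrols.
- **That one colour step always flips the haematuria result.** In Table 6-1 the step from 10 (negative) to 25 Eryt/µL (positive) exists only for haemolysed readings. The non-haemolysed rows go from 10 (negative) to 80 (positive).
- **That a false-positive rate can be attached.** This needs an assumed size of reading shift, which the documents do not give. The result would describe any open-label reading shift, not the effect of a story.

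The other side is also right that a blanket ban on passing results to participants or sites before lock would conflict with the plan. Section 9.1 has clinic dipsticks evaluated by the healthcare professional and bleeding discussed with them. Sections 17 and 19.5 require that subjects be told of new findings. Section 19.8 requires that investigators be told of problems leading to corrective action.

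**Conclusion.** The point holds as a cheap improvement. Section 22 expressly permits case stories during an open-label trial in which subjects record both secondary endpoints and several exploratory outcomes. Such stories could add expectation bias that the planned models would not separate from a device effect.

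The conclusion rests on the plan's approximate timings and on the possibility that a story is published early and seen by men still in the trial. The documents show neither event, and the size of any bias cannot be estimated from them.

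Section 22 also contradicts itself on identity. It allows a story to be public with the subject's consent, yet it requires that identification be impossible and says that subjects' identity stays confidential.

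**What to change.** In section 22:

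1. Replace the timing words at the end of the case-story sentence so that stories are allowed only after database lock.
2. Apply the embargo to case stories and promotional material only. Exempt safety communication, communication of new findings, and a subject's own clinical results.
3. Reconcile the option of a public story by consent with the rule against identification and the statement that identity stays confidential.

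If the internal publication policy already holds stories back until lock, cite that in section 22. This version is dated 24 March 2023 and lock was planned for January 2023. If data collection is over, the clinical investigation report should state whether any story appeared before lock.

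The cost is a short text edit and the sponsor's wait until database lock to use case stories. Sample size, significance level and study procedures do not change.
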